Skin and tissue inspections are conducted and study variables are collected daily by instructed researchers/research assistants/study nurses in agreement with the ICU and general ward staff. The following educational activities will be conducted before and during the trial:

- Initiation visit/kick-off meeting explaining the study design, procedures, data collection and documentation methods
- One hour skin and PU classification instruction, followed by an online examination PUCLAS3 (Beeckman, Schoonhoven 2014) for all study nurses/research assistants doing skin examinations
- Unannounced patient visits by the principle investigator for duplicate data collection and skin examination

Research assistants/study nurses/researchers follow up all included patients once daily for ensuring study compliance, monitoring correct dressing use and fit, doing skin inspections at the heels and sacral area and for monitoring the health condition including daily

documentation of PU risk and resource use regarding dressings and possible PU treatment (dressings, wound care procedures).

The study/follow-up ends if:

- The patient is no longer at “high” or “very high” PU risk according to the Charité standard (Figure 1) and if no sacral or heel PU developed or
- Complete healing of a within the study period developed heel or sacral PU or
- An adverse event (AE) related to the preventive dressings occurred or
- The patient wishes to withdraw or
- A severe form of protocol violation occurred (e.g. non-wearing of the dressings for more than 24 hours) or
- The patient dies or
- The patient is transferred to another care setting outside the Charité Campus Virchow or is discharged from the hospital

Adherence to the study protocol is improved using the following strategies:

- Kick-off meetings and training on the participating ICUs and EDs
- Subject cards at the bedside (Appendix 3)
- Once daily follow-up visits and assessments by researchers including checks of dressing fit
- Monthly status reports about recruitment on the participating wards
- Unannounced patient visits by the PI for duplicate data collection and skin examination

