### 3.6 Sample size

We are planning a study of independent cases and controls with 1 control per case. Prior data of the internal quality management indicate that the average PU incidence at the ICUs of the Charité is 0.06 per month. We expect that the cumulative PU incidence for experimental subjects will be 0.01 (RR 0.17). In order to test this hypothesis we will need to study 211 experimental patients and 211 control patients to be able to reject the null hypothesis that the PU incidence in the intervention and control groups is equal with a probability (power) of 0.8. The Type I error probability associated with this test of this null hypothesis is 0.05 (two-sided). We will use the chi-squared test statistic to evaluate this null hypothesis. To prevent a possible loss of follow-up of 10%, 464 patients in total are to be included. This total sample size is comparable to a previous trial using a similar intervention and design (Santamaria et al. 2013a). The “true” PU heel and sacral PU incidence in the study might be higher, because we will include only “high” and “very high risk” patients.

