**Figure 3. Data collection and management**

## 5.2 Statistical methods

Depending on the level of measurement (nominal, ordinal, continuous) variables will be described using absolute and relative frequencies or arithmetic means, medians and spread parameters (minimum, maximum, interquartile ranges, standard deviations). Baseline demographic (age, gender, PU risk etc.) and clinical characteristics (e.g. medical diagnoses, duration of ventilation) of each group will be displayed in a table.

The primary end point PU incidence category II, III, IV, DTI at heels and/or sacrum will be compared using a Chi-squared test. This will be the main analysis of this primary outcome. A logistic regression will be applied to adjust for baseline covariates. An alpha level of 5% (two-sided) will be applied. Kaplan-Meier analyses and logrank test will be used to compare the times to development of a new PU between groups. Multiple Cox regression analysis will be performed to adjust for potential confounders. Data will be analysed as intention to treat.

Secondary outcomes will be analysed in a similar way. Depending on the level of measurement (nominal, ordinal, continuous) secondary outcomes will be described using absolute and relative frequencies or arithmetic means, medians and spread parameters (minimum, maximum, interquartile ranges, SDs). Chi-squared or t-tests will be applied to compare groups. In case of normality assumption being violated, the Mann-Whitney U test will be used instead of t-test.

For daily measurements, missing values will be imputed via LOCF method, and the results will be compared to those without imputation.

A cost effectiveness analysis (CEA) comparing both groups will be conducted. Quantities of used preventive dressings including labor costs for application in the intervention group and quantities of used PU treatment materials (e.g. dressings, time) will be documented. Current market prizes in Euro will be used to calculate the total costs per group. An incremental cost effectiveness ratio (ICER) will be calculated by dividing the mean differences in costs by the mean differences in effects. In order to make results comparable a similar approach like the work by Santamaria et al. 2013b will be used.

All analytic steps including the CEA will be repeated for the two subgroups heel PUs and sacral PUs.

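### The planned Kaplan-Meier curves would overstate in-study ulcer incidence, by an amount the documents cannot fix; Aalen-Johansen curves should replace them

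*Combined protocol and SAP*

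**What the plan says.** Section 5.2 makes a chi-squared test the main analysis of the primary outcome. It then adds that "Kaplan-Meier analyses and logrank test will be used to compare the times to development of a new PU between groups", with a Cox model for adjustment. It gives no censoring rule, no competing-risk method and no time horizon for the curves. Secondary outcomes are to be handled similarly, and all steps are repeated for heel and sacral ulcers.

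Section 3.4 defines the primary outcome as the proportion of patients who develop an ulcer between baseline and end of study, and calls this the cumulative incidence.

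Section 3.3 lists what ends follow-up. The list includes "The patient dies or" and "The patient is transferred to another care setting outside the Charité Campus Virchow or is discharged from the hospital", and also loss of high or very high risk status in a patient without an ulcer. The remaining reasons are complete healing of an ulcer, a dressing-related adverse event, withdrawal, and a severe protocol violation, for which non-wearing of the dressings beyond 24 hours is the example.

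Section 7.3 says that ulcer risk peaks in the first days after admission.

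**The concern.** Kaplan-Meier estimates the risk that would apply if nobody left follow-up before an ulcer, and it assumes that those who leave carry the same later risk as those who stay. The exit list contradicts that assumption: a patient who has died cannot develop an ulcer, and a patient who leaves because risk has fallen has, by that criterion, a lower risk. These exits are also the usual outcome and ulcers the exception.

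One minus Kaplan-Meier is therefore a different and larger quantity than the cumulative incidence in section 3.4. The report would show two unequal incidences for one endpoint without explanation, and an absolute difference read from the curves would exceed the one the trial is designed to measure. The same holds for category I ulcers and for the heel and sacral analyses if they follow the same plan.

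**Working it through.** **1. The plan's own figure.** Section 3.6 states that "the average PU incidence at the ICUs of the Charité is 0.06 per month", expects 0.01 with dressings, and concludes that "we will need to study 211 experimental patients and 211 control patients" "with a probability (power) of 0.8" at two-sided 0.05. With pooled variance under the null and mean proportion 0.035:

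n = [1.96 × √(2 × 0.035 × 0.965) + 0.8416 × √(0.06 × 0.94 + 0.01 × 0.99)]² / 0.05² = 210.9, so 211 per arm.

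The total is 422 × 1.10 = 464, or 232 per arm. The figure reproduces. It rests on proportions alone and does not involve Kaplan-Meier.

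**2. Direction.** Let h₁ be the ulcer hazard and S₁ its survival function, and S₂ the probability of no ulcer-free exit. With ulcers and exits taken as independent, cumulative incidence is ∫h₁S₁S₂ and one minus Kaplan-Meier is ∫h₁S₁. As S₂ ≤ 1, the second is never smaller. The direction needs no figure for length of stay.

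**3. Size with constant hazards.** Inputs: final incidence c = 0.06 (control) and 0.01 (dressing), from section 3.6, read as end-of-stay proportions. Assumption: mean time to ulcer-free exit m (the mean stay) of 5 to 30 days, the same in both arms. The documents give only an expected minimum stay of three days.

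Exit hazard λ₂ = 1/m; ulcer hazard λ₁ = c / [(1 − c)m], so that λ₁/(λ₁ + λ₂) = c. Then

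1 − KM(t) = 1 − exp(−λ₁t); CIF(t) = c × [1 − exp(−(λ₁ + λ₂)t)]; expected number still ulcer-free and followed = 232 × exp(−(λ₁ + λ₂)t).

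Example, m = 10, day 30:
- Control: λ₁ = 0.006383; 1 − KM = 1 − exp(−0.1915) = 17.4%; CIF = 0.06 × (1 − exp(−3.191)) = 5.8%.
- Dressing: λ₁ = 0.001010; 1 − KM = 3.0%; CIF = 0.01 × (1 − exp(−3.030)) = 0.95%.
- Difference: 14.4 against 4.8 points, a factor of 3.0.

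Control arm:

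| Mean stay (days) | Day 14: 1 − KM / CIF | Factor | At risk of 232 | Day 30: 1 − KM / CIF | Factor | At risk of 232 |
|---|---|---|---|---|---|---|
| 5 | 16.4% / 5.7% | 2.9 | 12 | 31.8% / 6.0% | 5.3 | under 1 |
| 10 | 8.5% / 4.6% | 1.8 | 52 | 17.4% / 5.8% | 3.0 | about 10 |
| 15 | 5.8% / 3.8% | 1.5 | 86 | 12.0% / 5.3% | 2.3 | 28 |
| 30 | 2.9% / 2.3% | 1.25 | 141 | 6.2% / 3.9% | 1.6 | 80 |

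The difference between arms inflates by nearly the same factor in each row. The largest factors sit where almost nobody is left under observation.

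**4. Size with an early-peaking hazard.** Section 7.3 makes a constant hazard doubtful. Take an ulcer hazard A·exp(−t/τ), with A solved numerically so that final control incidence is 6%, and m = 10. Then 1 − KM(t) = 1 − exp[−Aτ(1 − exp(−t/τ))]. At day 30:

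| τ (days) | A per day | 1 − KM | CIF | Factor |
|---|---|---|---|---|
| 10 | 0.0125 | 11.2% | 6.0% | 1.9 |
| 5 | 0.0187 | 8.9% | 6.0% | 1.5 |
| 3 | 0.0269 | 7.8% | 6.0% | 1.3 |

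With less variable stays (gamma shape 4), mean stay 15 days and τ = 3, the values are 6.2% and 6.0%, a factor of about 1.04.

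**5. Logrank test.** In 4,000 simulated null trials with 232 per arm, and exits equal across arms and unrelated to ulcer risk, the logrank test rejected in 4.7% and the chi-squared test in 4.5%. The test keeps its level under those conditions.

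**The case against.** The strongest case against is that this changes nothing that matters. The main analysis is a chi-squared test of the crude proportion, which is already an end-of-stay cumulative incidence. The sample size and the conditional-power rule in section 6.2 also concern incidences. Section 5.2 names Kaplan-Meier for comparing times, and plans no risk, risk difference or number needed to treat from the curves. All of this stands, and it confines the point to the supportive analyses.

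A second argument is that the target is a choice: discharge and loss of risk status do not make an ulcer impossible, so one could aim for the risk had patients stayed at high risk. That stands in part. But for that target these exits are informative censoring, so plain Kaplan-Meier would not estimate it reliably either. For the in-study target of section 3.4 they are competing events.

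A reader might infer three stronger things. The first is that the curves will overstate risk several-fold. That needs a roughly constant hazard and a horizon of about three or more mean stays; the documents give neither, and section 7.3 points to smaller factors. The second is that the plan states that these exits are censored. It does not; this is what a standard Kaplan-Meier analysis does by default. The third is that the logrank and Cox comparisons are invalid. They remain usable as cause-specific comparisons if exits are not differential.

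**Conclusion.** The concern holds for the time-to-ulcer curves and should be corrected, but it does not threaten the primary result. If ulcer-free exits are censored in the standard way, one minus Kaplan-Meier overstates in-study incidence in both arms. In every scenario examined with equal exits in the two arms, it also inflates the absolute difference.

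The size cannot be fixed from the documents. It runs from close to 1 (strongly early hazard, less variable stays) to about 5 (constant hazard, mean stay 5 days, day 30). These factors rest on the assumed stays, on final incidences of 6% and 1%, and on equal exit patterns. No single factor should be quoted as the expected bias.

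Equal exit is itself uncertain: follow-up can end for a dressing-related adverse event or for non-wearing only in the dressing arm. The documents do not show how often, so differential exit is something to check, not an established bias.

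**What to change.** For the time-to-ulcer display, replace the Kaplan-Meier curves with Aalen-Johansen cumulative incidence curves by arm. Treat death, discharge or transfer, and end of high-risk status as competing events, and print the numbers at risk. State in the SAP how each remaining exit in section 3.3 is handled. Keep the logrank test and Cox model, labelled as cause-specific; Gray's test is optional. Tabulate exits by reason and arm.

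Confirm that the CRF captures date and reason of exit. The tables in section 3.4 list no such item, although daily visits and daily risk scoring should make it recoverable.

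The cost is some SAP wording, a little extra analysis, and two effect scales to explain. The primary test and sample size do not change.

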### Secondary objectives

- To determine if preventive silicone dressings (Mepilex® border) applied to the heels and to the sacrum in addition to PU standard prevention reduce the PU incidence density category II, III, IV, and deep tissue injury (DTI) compared to PU standard prevention alone in at high or very high risk hospital patients.
- To determine if preventive silicone dressings (Mepilex® border) applied to the heels and to the sacrum in addition to PU standard prevention reduce the cumulative PU incidence category I compared to PU standard prevention alone in at high or very high risk hospital patients.
- To determine if preventive silicone dressings (Mepilex® border) applied to the heels and to the sacrum in addition to PU standard prevention reduce the PU incidence density category I compared to PU standard prevention alone in at high or very high risk hospital patients.
- To determine if preventive silicone dressings (Mepilex® border) applied to the heels and to the sacrum in addition to PU standard prevention increase days free of PUs category I, and category II, III, IV, and DTI compared to PU standard alone in at risk hospital patients.
- To determine if preventive silicone dressings (Mepilex® border) applied to the heels and to the sacrum in addition to PU standard prevention are cost effective.

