## Secondary outcomes

Name	Method and metric	Time points of data collection
Pressure ulcer category II, III, IV, Unstageable, DTI at heels or sacrum	
 
• Clinical assessment using the NPUAP PU classification system
 
• Proportions developed per 1000 bed days (incidence)
 
	D0 and once daily
Pressure ulcer category I (non-blanchable erythema) at heels and/or sacral area	
 
• Clinical assessment using the NPUAP PU classification system
 
• Proportions developed from baseline until end of study (cumulative incidence)
 
	D0 and once daily
Pressure ulcer category I (non-blanchable erythema) at heels and/or sacral area	
 
• Clinical assessment using the NPUAP PU classification system
 
• Proportions developed per 1000 bed days (incidence)
 
	D0 and once daily
Days free of sacral and/or heels pressure ulcers category I, II, III, IV, DTI	
 
• Clinical assessment using the NPUAP PU classification system
 
• Number
 
	D0 and once daily
Resources associated with heel and sacral PU prevention	
 
• Preventive dressings (n), time for dressing application (minutes; data source: estimation)
 
• Type of support surface (standard, special elastic foam, viscoelastic foam, low air loss overlay/mattress, alternating air mattress; data source: clinical records and direct observation)
 
• Type of turning (30° degrees left/right, supine, prone, other; data source: clinical records)
 
	D0 and once daily
Resources associated with heel and sacral PU treatment	
 
• Wound assessments (number and times; data source: clinical records and estimation)
 
• Wound infection diagnoses, e.g. swabs, biopsies (number, times; data source: clinical records and estimation)
 
• Therapeutic primary and secondary dressings (numbers, types), time for dressing application/changes (minutes; data source: clinical records and estimation)
 
• Debridement (numbers and types incl. material; data source: clinical records and estimation)
 
• Systemic antimicrobial treatment because of PU wound (number, types; data source: clinical records)
 
	D0 and once daily

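### No person-time comparison is specified for the two incidence-density outcomes, and the tests stated for secondary outcomes ignore or mis-weight patient-days

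*Combined protocol and SAP*

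**What the plan says.** Section 2.2 lists two density objectives: to "reduce the PU incidence density category II, III, IV, and deep tissue injury (DTI", and to "reduce the PU incidence density category I compared to PU standard prevention alone". The secondary outcomes table in 3.4 gives the metric for both as "Proportions developed per 1000 bed days (incidence".

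Section 5.2 opens its paragraph on secondary outcomes with "Secondary outcomes will be analysed in a similar way". It then states that "Chi-squared or t-tests will be applied to compare groups", and adds: "In case of normality assumption being violated, the Mann-Whitney U test will be used instead of t-test". The preceding paragraph, on the primary outcome, says that "Kaplan-Meier analyses and logrank test will be used to compare the times to development of a new PU between groups" and that "Multiple Cox regression analysis will be performed to adjust for potential confounders".

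No rate ratio, Poisson-type model or other comparison of events over summed bed days appears in the plan. It also does not say whether bed days after a first ulcer count, or whether a patient can contribute more than one ulcer.

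Under 3.3, follow-up ends on individual events (loss of high-risk status, discharge or transfer, death, withdrawal and others), not at a fixed day. Two of the end rules, a dressing-related adverse event and the dressings being off for more than 24 hours, can in practice arise only in the intervention arm. A patient who develops an ulcer is followed on until it heals.

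**The concern.** A density is a count of events divided by total time at risk. Its purpose is to allow for unequal observation time.

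- **Chi-squared** divides by patients, not days, so it repeats the cumulative-incidence comparison.
- **The t-test** needs one rate per patient. An ulcer on day 2 scores 1/2 = 500 per 1000 days and one on day 20 scores 1/20 = 50, while every ulcer-free patient scores 0 whether seen for 3 days or 30. The mean of such values is not events over days.
- **Mann-Whitney U** is where the plan's normality rule leads, because most patients score 0. With so many ties it mainly compares the share of patients with an ulcer, as chi-squared does.

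If bed days differ between arms, a difference in observation time can therefore be reported as a difference in rate. If dressing patients are observed for longer, a real benefit can be diluted.

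**Working it through.** **1. The plan's own figure.** Section 3.6 gives 0.06 v 0.01, two-sided alpha 0.05, power 0.8. With pooled variance and mean proportion 0.035:

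n = [1.96·√(2·0.035·0.965) + 0.8416·√(0.06·0.94 + 0.01·0.99)]² / 0.05² = 210.9, so 211 per arm, as stated. With 10% added, 211 × 1.10 = 232 per arm, or 464. This is for the primary test; the documents give no figure for the density outcomes.

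**2. Assumptions.** The documents give no follow-up length. Assumed: control mean 10 days, intervention mean 5 to 15. The daily rate is also assumed: 0.0062 (0.0064 in one set of runs) gives about 6% cumulative over such follow-up. Section 3.6 states 0.06 per month, which read literally is 0.06/30 = 0.002 per day, so that is run too. Section 3.6 adds that incidence among the high-risk patients enrolled might be higher.

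**3. Ties.** At the planning incidences, 211 × 0.06 + 211 × 0.01 = 12.7 + 2.1 = 14.8 patients have an ulcer. About 407 of 422 (96%) then share the value 0.

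**4. Hand check of chi-squared at equal true rates.** With a constant rate λ and gamma follow-up (shape 2, mean m), the expected proportion with an ulcer is P(m) = 1 − (1 + λm/2)⁻². At λ = 0.0062: P(10) = 0.0592, P(7) = 0.0420, P(5) = 0.0303. Equal rates thus give unequal proportions.

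- 10 v 7 days: difference 0.0172, standard error 0.0213. Rejection = Φ((0.0172 − 1.96·0.0213)/0.0213) + Φ((−0.0172 − 1.96·0.0213)/0.0213) ≈ 0.127.
- 10 v 5 days: difference 0.0289, standard error 0.0201. The same formula gives about 0.30.

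**5. Simulated rejection at equal true rates** (211 per arm; 2,000 to 4,000 trials per scenario; gamma or exponential follow-up; ranges span the runs; nominal 5%).

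| Mean days, control v dressing | Chi-squared and Mann-Whitney, 0.0062–0.0064/day | Person-time test, same rates | Chi-squared, 0.002/day |
|---|---|---|---|
| 10 v 10 | 5% | 5% | – |
| 10 v 9 | about 5% | 4–5% | – |
| 10 v 8 | 7–8% | 4–5% | – |
| 10 v 7 | 11–13% | 4–5% | about 6% |
| 10 v 5 | 26–30% | 5% | about 11% |

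The t-test on per-patient rates stayed between 3.5% and 6.6% at 0.0062–0.0064 per day. Log-rank stayed between 4.6% and 5.3%.

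**6. Power at the planning effect** (control rate 0.0062–0.0064, dressing rate about one sixth of it).

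- Equal follow-up: chi-squared and Mann-Whitney about 84%, log-rank 85%, person-time 84–87%, t-test 48–63%.
- 10 v 15 days: chi-squared 70–73%, person-time 92%.

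**7. The counting rule.** If all ulcers are counted, events cluster within patients. Suppose each patient with an ulcer has a 30% chance of one at each of two further sites (an assumption). Ulcers per affected patient then have mean 1.6 and mean square 2.98, so the variance is 2.98/1.6 = 1.86 times the Poisson value. A nominal 5% test rejects about 2Φ(−1.96/√1.86) = 15% of the time; a simulated mid-p test rejected 13%. Days spent healing, if counted, enlarge the denominator of the arm with more ulcers and pull the ratio toward 1.

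**The case against.** The strongest reply is that "Secondary outcomes will be analysed in a similar way" brings over everything in the primary-outcome paragraph, including log-rank and Cox. Both allow for unequal time at risk up to the first ulcer, and log-rank held its level in every scenario. A reader might infer that chi-squared, t and Mann-Whitney are the only tests available for density; the documents do not support that. What stands is ambiguity. Log-rank is tied to time to a new ulcer, neither method gives a rate per 1000 bed days, and the sentences that follow name other tests. An analyst could defend any of several after seeing the data.

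A reader might also infer that all the stated tests are invalid. With balanced bed days, chi-squared and Mann-Whitney lose neither level nor power. The t-test's fault is mainly lost power, and the plan's normality rule would probably replace it anyway.

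Finally, nothing in the documents predicts a 30–50% gap in mean follow-up. They show that follow-up can differ by arm, not that it will. At 10 v 9 days the error is hardly changed, and at 0.002 per day even the large gaps do much less harm. These limits reduce the likely size of the problem. They do not supply the missing comparison.

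**Conclusion.** The point holds in a limited form. Two secondary outcomes are defined per bed day, no person-time comparison is specified for them, and the tests stated for secondary outcomes do not use patient-days properly. The size depends on the imbalance in follow-up and on the event rate, both assumed here: negligible at 10 v 9 days, moderate at 10 v 8 to 10 v 7 if the rate is near 0.0062 per day, and serious only at gaps such as 10 v 5.

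It would be wrong to carry this over to the primary result. The primary outcome is a cumulative proportion with its own chi-squared test; that test, the 211 per arm and the total of 464 are untouched. This should be corrected before analysis, but it does not threaten the main conclusion.

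**What to change.** In 5.2, add a rule of this kind:

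*Incidence densities (category II and above as defined in 3.4, and category I) are compared by the rate ratio with 95% CI. The numerator is the first qualifying ulcer per patient. The denominator is at-risk patient-days, from baseline to the first qualifying ulcer or the end of follow-up. The test is the exact conditional mid-p test, or Poisson regression with log(at-risk days) as offset. Chi-squared, t-test and Mann-Whitney U are not used for these outcomes.*

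Choose one of the two tests in advance. If all ulcers are to be counted instead, use a patient-level robust variance or a negative-binomial model. State whether log-rank and Cox also apply to secondary outcomes, and report total at-risk days by arm so that any imbalance is visible.

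The cost is wording only. Skin status is assessed daily from baseline, so events and days are already collected, and no change to sample size or conduct is needed.

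### LOCF scores patients lost while ulcer-free as non-events, and no planned analysis tests whether the loss was related to ulcers nobody saw

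*Combined protocol and SAP*

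**What the plan says.** Section 5.2 deals with missing data in one sentence. For daily measurements, "missing values will be imputed via LOCF method", and the results are to be compared with those obtained without imputation. The section does not say which daily variables are meant, whether only gaps between visits are filled, to what day a value is carried, or who is in the denominator when nothing is imputed.

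Section 3.4 schedules ulcer assessment at D0 and once daily, so the rule covers the primary outcome (cumulative incidence from baseline to each patient's end of study). It also covers days free of ulcers and the incidence density, whose metric reads "Proportions developed per 1000 bed days (incidence)".

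Section 3.6 gives the loss allowance: "To prevent a possible loss of follow-up of 10%, 464 patients in total are to be included".

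Section 3.3 sets no fixed follow-up horizon. Among the events that end follow-up are an adverse event related to the dressing and a severe protocol violation, for which the example is prolonged non-wearing of the dressing.

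Section 5.2 also plans Kaplan-Meier, logrank and Cox analyses and an intention-to-treat analysis. It plans no tipping-point, worst-case or multiple-imputation analysis.

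**The concern.** Section 3.2 excludes patients with an existing sacral or heel ulcer, and few ulcers are expected. The last recorded status of most lost patients will therefore be ulcer-free, and carrying it forward makes them non-events. Analysing without imputation either drops these patients, which assumes they had the same risk as those who stayed, or keeps them as non-events, which reproduces the LOCF result for the primary proportion. Neither option allows for lost patients having developed ulcers more often.

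In many trials that would be a minor gap. Here the expected ulcers are so few that a handful of unseen ones can move the primary test across 0.05. The dressing-related adverse event rule, and the example given for the protocol-violation rule, can apply only in the intervention arm. Balanced and ignorable loss therefore cannot be taken for granted.

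**Working it through.** **1. The plan's own figures.** Inputs from section 3.6: control rate 0.06 ("average PU incidence at the ICUs of the Charité is 0.06 per month"), dressing rate 0.01, power 0.80, two-sided alpha 0.05, chi-squared test.

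n per arm = [z₀.₉₇₅ √(2p̄(1−p̄)) + z₀.₈₀ √(p₁(1−p₁) + p₂(1−p₂))]² / (p₁−p₂)², with p̄ = 0.035

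= [1.960 × √0.06755 + 0.842 × √0.0663]² / 0.0025 = 210.9, so 211, as stated. Then 422 × 1.10 = 464.2, so 464, or 232 per arm.

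**2. Expected ulcers against expected loss.** Expected ulcers: 232 × 0.06 + 232 × 0.01 = 13.9 + 2.3, about 16. Expected loss: 232 × 0.10, about 23 per arm.

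**3. What each planned analysis can see.** Let p be the ulcer risk during observation, d the proportion lost, and k the risk of lost patients relative to the rest. Assume that ulcers in lost patients arise after the last visit.

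- LOCF proportion: p(1−d)
- Lost patients dropped: p
- Truth: p(1−d) + kpd

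The loss splits and k below are assumptions; the documents give only the 10% overall. Take p = 0.06 in both arms, so that the dressing has no effect during observation:

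| Loss, control / dressing | k | True RR | LOCF RR | RR, lost dropped |
|---|---|---|---|---|
| 5% / 15% | 1 | 1.00 | 0.895 | 1.00 |
| 5% / 15% | 2 to 3 | 1.10 to 1.18 | 0.895 | 1.00 |
| 0% / 20% | 1 | 1.00 | 0.80 | 1.00 |
| 0% / 20% | 2 to 3 | 1.20 to 1.40 | 0.80 | 1.00 |

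Example, last row with k = 2: truth (0.048 + 0.024)/0.06 = 1.20; LOCF 0.048/0.06 = 0.80.

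With k = 1 the comparison reveals the LOCF bias. With k above 1 it shows exactly the same pair of results, so it cannot tell the two situations apart, and both estimates miss the harm.

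If 10% are lost from each arm at the planned rates, LOCF gives 5.4% versus 0.9%. The RR stays at 0.167, and power at 232 per arm is 0.79 instead of 0.84.

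**4. Sensitivity of the primary test.** Assume 13 control and 2 dressing ulcers observed (close to 6% and 1% of the 209 per arm who remain) and 23 lost per arm. For a versus b ulcers with n per arm, the uncorrected statistic is

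X² = 2n(a−b)² / [(a+b)(2n−a−b)].

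- LOCF, n = 232: 464 × 121/(15 × 449) = 8.34, p = 0.0039
- Lost dropped, n = 209: 418 × 121/(15 × 403) = 8.37, p = 0.0038

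The planned check would look reassuring. Now add unseen ulcers among the lost, with n = 232:

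| Control total | Dressing total 2 | 3 | 4 | 5 | 6 |
|---|---|---|---|---|---|
| 13 (none added) | 0.0039 | 0.011 | 0.026 | 0.054 | 0.101 |
| 14 (one added) | 0.0023 | 0.0066 | 0.016 | 0.035 | 0.067 |
| 16 (three added) | 0.0008 | 0.0023 | 0.0061 | 0.014 | 0.029 |

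Example, 13 versus 5: 464 × 64/(18 × 446) = 3.70, p = 0.054. Starting from 12 or 14 observed control ulcers, with none added among lost controls, the tipping point is three or four added dressing ulcers.

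**5. Bed-days.** These change only if status is carried past the last visit. Assume lost patients were observed for a fraction f of their stay, f = 0.25 to 0.50. Observed time is then (1−d) + df of the full stay, and with no true effect the LOCF density ratio is the ratio of these between arms. It is 0.92 to 0.95 for 5% / 15% loss and 0.85 to 0.90 for 0% / 20%, against 1.00 on observed days.

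**The case against.** Several points on the other side have force.

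A reader might infer that LOCF necessarily adds unobserved bed-days. The documents do not say so. Section 5.2 names no day to carry to, and section 3.3 makes death, discharge and transfer defined ends of follow-up, not missing days. If LOCF only fills gaps within a stay, the bed-days are real and only the ulcer status on them is unobserved. This objection stands.

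A reader might also infer that the planned comparison can reveal no bias at all. That is too strong. If lost patients are dropped, it shows unequal loss at equal risk, and it would show added bed-days too. The unimputed Kaplan-Meier analysis would censor at the last visit. What remains is that all of these assume loss unrelated to unseen ulcer risk.

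Next, LOCF is not the sole cause. A patient who leaves ulcer-free is a non-event in the primary proportion even without imputation, unless removed from the denominator. That is correct, and it means that deleting LOCF is not enough by itself. LOCF also does not reach everyone: a patient with an observed ulcer stays an event, and section 7.3 has data deleted when consent is refused.

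Finally, the 13 versus 5 example is one-sided. Three ulcers in 23 is 13%, more than twice the planned control rate. The binomial chance of three or more is 0.15% at 1% risk and 16% at 6%. At 6%, 23 patients yield about 1.4 ulcers (23 × 0.06), so comparing the number lost with the number of events overstates the danger if read literally. Adding three control ulcers as well (16 versus 5) gives p = 0.014. The example shows sensitivity; it is not a forecast.

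**Conclusion.** The concern holds in limited form. The LOCF rule is underspecified for an event outcome with patient-specific follow-up, it scores patients lost while ulcer-free as non-events, and no planned analysis addresses loss related to unseen ulcer risk.

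Under the assumed counts, significance is lost with three unseen dressing-arm ulcers if lost controls had none, and with four if they had one (14 versus 6, p = 0.067). LOCF and the analysis with the lost dropped would both report p = 0.004 throughout. The event counts, the 23 lost per arm and the split of unseen ulcers are assumptions built on the plan's two rates and its 10% allowance.

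The documents do not support saying that the result would be overturned, or that loss will in fact differ by arm. They show only that two rules for ending follow-up make such a difference possible, and that the plan has no way to show how much it would matter.

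**What to change.** In section 5.2:

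1. Do not impute ulcer status by LOCF, and name any other daily variables to which LOCF still applies.
2. For incidence density, time to ulcer and days free of ulcers, count time only to the last skin inspection.
3. State the denominator of the no-imputation analysis of the primary proportion: all randomised patients, or only those with complete follow-up, with a definition of lost.
4. Add a two-way tipping-point table for the primary proportion, varying the number of unseen ulcers among lost patients in both arms, and report the number lost and the reasons by arm.

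Multiple imputation may be added but is not the main remedy. In its standard form it also assumes ignorable loss, and within an arm expecting about two ulcers it would be unstable.

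The cost is some SAP wording and a modest extra analysis, with no new data. The downside is that the table may show the conclusion to be less robust than a single p-value suggests.
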